4.2. Inclusion Criteria

Subjects will be eligible for participation in the study only if they meet ALL of the following inclusion criteria:

1. Scheduled to undergo an elective (non-emergent) bowel resection with a planned stoma via laparotomy or minimally invasive technique. This includes any subject in which a resection of the small intestine, colon, or rectum is performed for any elected indication.
2. Planned stoma takedown or other planned abdominal surgery within 8 months of the initial surgery.
3. Willing to perform and comply with all study procedures including attending clinic visit as scheduled and completion of a second surgery for stoma takedown or other abdominal surgery and to determine the presence of intra-abdominal adhesions.
4. Has been informed of the nature of the study (either the subject or their legal representative), agrees to its provisions, and has provided written informed consent.

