6.16. Adhesions Assessment (Day 0 and at time of second surgery)

The surgeon will determine the incidence, extent, and severity of adhesions at the time of surgical closure for the first surgery and at the time of opening for the second surgery. Grading of the adhesions (extent and severity) will be performed by the surgeon during the surgical procedure ([Appendix 5](#)).

For each abdominal region, the score of the extent and severity of adhesions are evaluated. The surgeon will grade the intra-abdominal adhesions at 9 abdominal region (right upper, epigastrium, left upper, left flank, left lower, pelvis, right lower, right flank and central) and when appropriate at 4 areas around the ostomy (superior, lateral, inferior, and medial). ([Coccolini et al., 2013](#), [Dabrowski et al., 2016](#), and the [Seprafilm Package Insert](#)).

For each abdominal region, extent of adhesion formation is scored for adhesions from the abdominal wall to bowel (including abdominal wall to viscera) and for adhesions from bowel to bowel (including bowel to viscera) as follows:

- 0 = no adhesion;
- 1 = minimal (<1/3 of the site is covered);
- 2 = moderate (1/3 to 2/3 of the site is covered), or
- 3 = extensive (>2/3 of the site is covered).

The severity of the adhesions in the region are graded using the following score:

- 0 = no adhesions;
- 1 = filmy thickness, avascular;
- 2 = moderate thickness, limited vascularity, or
- 3 = dense thickness, vascularized.

At the second surgery visit the site study staff will determine if the subject experienced a hospital readmission due to GI concerns and/or other medical reasons. If readmission did occur, this event should be recorded as a SAE.

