6.17. Appropriateness of Measurements

All procedures used to measure the safety and efficacy of LB1148 in this study are considered to be appropriate and necessary to obtain the required safety, tolerability, and efficacy data. The safety assessments used in this study, such as physical examination, vital signs, opioid use, laboratory assessments, and GI function assessments are widely used and are considered appropriate for monitoring subjects' health and well-being in this type of study. The measure used to evaluate pain levels is a validated and widely accepted rating scale used for clinical studies evaluating pain.

ADVERSE EVENTS ASSESSMENTS

AE data will be collected from first administration of study drug through Day 14, Hospital Discharge, or study termination, whichever comes first. Following discharge through the second surgery visit, any hospital readmissions will be recorded as SAEs.

AEs/SAEs related to the second surgery will also be collected.

Investigators are responsible for monitoring the safety of subjects who have entered this study and for alerting the Sponsor or its designees to any event that seems unusual, even if this event may be considered an unanticipated benefit to the subject.

The Investigator is responsible for the appropriate medical care of subjects during the study. The Investigator remains responsible for following, through an appropriate health care option, SAEs or AEs that caused the subject to discontinue before completing the study. The subject should be followed until the event is resolved or explained. Frequency of follow-up evaluation is left to the discretion of the Investigator.

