7.1. Adverse Events

An AE is any untoward medical occurrence in a subject administered a drug or biologic (medicinal) product; the event does not necessarily have a causal relationship with the administration of the study drug. An AE can therefore be any unfavorable and unintended sign (including a clinically significant abnormal laboratory finding), symptom, or disease temporally associated with the use of a study drug, whether or not considered related to the study drug.

This includes any side effect, injury, toxicity, or sensitivity reaction, and may include a single symptom or sign, a set of related symptoms or signs, or a disease. An AE may also be any laboratory abnormality judged to be clinically significant by the Investigator that worsened when compared to baseline.

AEs include the following:

- All suspected adverse drug reactions.
- All reactions from medication overdose, abuse, withdrawal, sensitivity, or toxicity.
- Apparently unrelated illnesses, including the worsening of a pre-existing illness.
- Injury or accidents.
Note: If a medical condition is known to have caused the injury or accident (e.g., a fall secondary to dizziness), the medical condition (dizziness) and the accident (fall) should be reported as 2 separate AEs.
- Abnormalities in physiological testing or physical examination (findings that require clinical intervention or further investigation beyond ordering a repeat [confirmatory] test).

- Laboratory abnormalities that are clinically significant and require clinical intervention or further investigation (beyond ordering a repeat [confirmatory] test) unless they are associated with an already reported clinical event.

An AE **does not** include:

- Medical or surgical procedures (e.g., surgery, endoscopy, tooth extraction, transfusion); the condition that leads to the procedure is an AE.
- Pre-existing diseases or conditions present or detected at screening/baseline that do not worsen in severity or frequency.
- Situations where an untoward medical occurrence has not occurred (e.g., hospitalization for elective surgery, social and/or convenience admissions).
- Overdose of either study drug or concomitant medication without any signs or symptoms.

Throughout the course of the study, every effort should be made to remain alert to possible AEs. Subjects should be encouraged to report AEs spontaneously or in response to general, non-directed questioning.

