7.9. Adverse Event Reporting Period

AE data will be collected from first administration of study drug through Day 14, Hospital Discharge, or study termination, whichever comes first. Following discharge through the Month 3 visit, any hospital readmissions will be recorded as SAEs.

AEs/SAEs related to the second surgery will also be collected.

If a subject experiences an AE after signing informed consent, but prior to receiving study drug, the event will NOT be collected unless the Investigator feels the event may have been caused by a protocol procedure.

In addition, any known untoward event that occurs subsequent to the AE-reporting period that the Investigator assesses as related to the study drug should also be reported as an AE.

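### The rule that any readmission is an SAE (Protocol 7 and 7.9) contradicts 7.1 and 7.2 and has two different end points, so sites may code planned admissions differently

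*Protocol*

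**What the plan says.** The protocol states a readmission rule in several places.

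- **Section 7, opening text:** "Following discharge through the second surgery visit, any hospital readmissions will be recorded as SAEs". There is no exception.
- **Section 7.9:** "Following discharge through the Month 3 visit, any hospital readmissions will be recorded as SAEs". The rule is the same, but the end point differs. Section 7.13 also ends SAE reporting at Month 3.
- **Sections 6.15 and 6.16:** at Day 30 and at the second surgery visit, staff "determine if the subject experienced a hospital readmission due to GI concerns and/or other medical reasons". Section 6.16 then adds: "If readmission did occur, this event should be recorded as a SAE".
- **Appendix 1:** footnote 13 (Day 30 call) equates readmissions with SAEs. Footnote 14 (second surgery) limits recording to events related to the surgical procedure.

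The definitions are in Sections 7.1 and 7.2. Among the things that are not AEs, 7.1 lists "Situations where an untoward medical occurrence has not occurred (e.g., hospitalization for elective surgery, social and/or convenience admissions" and "Medical or surgical procedures (e.g., surgery, endoscopy, tooth extraction, transfusion); the condition that leads to the procedure is an AE". Section 7.2 defines an SAE as an AE with one of the listed outcomes, and 7.10 sends only events meeting that definition to the SAE Report.

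Inclusion criterion 2 requires "Planned stoma takedown or other planned abdominal surgery within 8 months of the initial surgery". SAP 12.1 tabulates serious AEs by system organ class and preferred term in the Safety Population, and does not mention planned admissions.

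**The concern.** The design itself schedules a later operation for every subject enrolled under the current criteria. Appendix 9 explains that the longer window leaves time for cancer treatment, so other scheduled admissions are foreseeable, although the documents do not count them. A site that follows the wording of Section 7 could report such an admission as an SAE, while a site that follows 7.1 and 7.2 would not.

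This matters because routine AE collection stops at Day 14, discharge or termination, whichever comes first. After that, the record consists mainly of readmissions, POI up to Day 30, events related to the second surgery, and late events judged related to study drug. Planned admissions mixed into the readmission SAEs would raise the totals in both arms and make a real difference harder to see. They could also create a difference if sites or arms differ in how many are recorded.

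**Working it through.** The documents state no SAE or readmission rate, so there is no figure to reproduce. The check is a reading of the text, followed by an illustration on assumed rates.

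**Step 1. Three test cases against the literal text**

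| Rule | Scheduled admission at month 2, nothing untoward | Takedown admission at month 6, nothing untoward | Unplanned admission at month 6 for a medical event |
|---|---|---|---|
| Section 7 | SAE | SAE if the window includes that admission | SAE |
| Section 7.9 | SAE | Outside the window | Outside the window |
| Section 6.16 | Depends on whether a scheduled stay has a medical reason | Unclear; it seems to ask about earlier stays | SAE |
| Footnote 14 | Not recorded at the second surgery visit | Only procedure-related events recorded | Recorded at that visit only if procedure-related |
| Sections 7.1 and 7.2 | Not an AE, so not an SAE | Not an AE, so not an SAE | SAE (re-hospitalization) |

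No case gets the same answer from every row. The first column shows the contradiction most plainly. The last shows that the mismatch in windows also leaves it unclear whether a genuine late readmission is captured.

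**Step 2. Size if planned admissions are recorded**

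Let *p* be the true risk of at least one SAE in an arm. Let *g* be the share of subjects with a planned admission recorded as an SAE, equal in both arms and independent of *p*. Then:

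recorded risk = *p* + (1 − *p*) × *g*

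Assumed true risks are 15% and 30%. For example, at *g* = 10%: 0.15 + 0.85 × 0.10 = 0.235 and 0.30 + 0.70 × 0.10 = 0.370.

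| *g* | Lower-risk arm | Higher-risk arm | Risk ratio | Difference (points) |
|---|---|---|---|---|
| 0 | 15.0% | 30.0% | 2.00 | 15.0 |
| 10% | 23.5% | 37.0% | 1.57 | 13.5 |
| 30% | 40.5% | 51.0% | 1.26 | 10.5 |
| 50% | 57.5% | 65.0% | 1.13 | 7.5 |
| 80% | 83.0% | 86.0% | 1.04 | 3.0 |

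**Step 3. Limit set by the analysis population**

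The serious-AE table uses the Safety Population, which includes subjects from before 01Jan2022. SAP 4.1 says their second surgery was optional. Assume 30 current subjects (the SAP 4.3 minimum) and 55 earlier ones (the middle of the 50-60 planned for the interim analysis), 85 in all.

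- If no earlier subject had a second surgery and every current takedown were recorded, *g* = 30/85 = 0.353. The recorded risks are 0.15 + 0.85 × 0.353 = 0.450 and 0.30 + 0.70 × 0.353 = 0.547, a ratio of 1.22.
- If half of the earlier subjects had one and all were recorded, *g* = 57.5/85 = 0.676. The risks are 0.725 and 0.774, a ratio of 1.07.

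Both bullets assume recording at every site, which is the extreme case.

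**Step 4. Which rows move**

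SAP 12.1 counts a subject once per preferred term and once per system organ class. A planned-admission record therefore affects any overall total, the class to which it is coded, and its own term. Preferred-term rows for real events do not change.

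**The case against.** A reader might infer that the takedown admission itself will enter the SAE table for every subject who completes. The documents do not support that. Section 7.1 rules out elective-surgery admissions and procedures, 7.10 restricts the SAE Report to events that meet 7.2, and the second surgery has its own rule for related AEs and SAEs, which would make little sense if the admission already counted. Section 6.16 asks at that visit whether a readmission has occurred, which reads most naturally as an earlier one. Under 7.9, a takedown after Month 3 is outside the window altogether.

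A reader might also infer that 6.16 makes every readmission an SAE. It is limited to GI concerns or other medical reasons, as is 6.15. A third tempting inference is that the any-SAE comparison could lose all information. That needs nearly every subject to have a planned admission recorded, which does not fit a Safety Population containing earlier subjects whose second surgery was optional. Moreover, the SAP plans frequency tables and no SAE test or risk ratio.

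All of this stands, and it limits the point to a risk created by the literal text. It does not remove the contradiction. Sections 7 and 7.9 still say any readmission without exception, footnote 13 supports that reading, and no passage says which rule prevails.

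**Conclusion.** The contradiction holds. The rule in Sections 7 and 7.9 conflicts with the definitions in 7.1 and 7.2 and is broader than 6.15 and 6.16. Its window is also inconsistent: the second surgery visit in Section 7, and in 7.9 and 7.13 a Month 3 time point that the current schedule does not contain. The consequence is conditional. If some sites follow the literal wording and others the definitions, the any-SAE total and the affected class totals would be inflated unevenly.

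The size cannot be estimated from the documents. The ratios above rest on assumed risks, an assumed recording share that is equal in both arms, and, for the pooled cases, an assumed 85 subjects. They show only that a modest share can matter: 10% is enough to move a ratio of 2.0 to 1.57. The point is worth correcting because the current cohort is small and readmission SAEs form much of the safety record after discharge.

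**What to change.** **Protocol.** Reconcile Sections 6.15, 6.16, 7, 7.9 and 7.13 and Appendix 1 footnotes 13 and 14 with Sections 7.1, 7.2 and 7.10. One readmission rule and one reporting window should apply throughout, and planned admissions without an untoward event should be handled consistently with 7.1.

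**SAP 12.1.** State, before final unblinding, how SAE records that consist only of a planned admission are treated. Identify them from the admission reason and second-surgery date, through a review by people who do not know the treatment assignment. The reviewers need to be chosen with care, because Protocol 5.5 foresaw sponsor-side unblinding at the interim analysis and SAP 14 reports that interim tables went to the sponsor. Show these records in a separate listing and leave them out of the serious-AE totals, or present the totals with and without them.

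**Cost.** Wording changes in both documents and a blinded review of the SAE records already entered. The small downside is a planned or unplanned judgement for each admission; showing totals both ways makes the effect of that judgement visible.

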7.1. Adverse Events

An AE is any untoward medical occurrence in a subject administered a drug or biologic (medicinal) product; the event does not necessarily have a causal relationship with the administration of the study drug. An AE can therefore be any unfavorable and unintended sign (including a clinically significant abnormal laboratory finding), symptom, or disease temporally associated with the use of a study drug, whether or not considered related to the study drug.

This includes any side effect, injury, toxicity, or sensitivity reaction, and may include a single symptom or sign, a set of related symptoms or signs, or a disease. An AE may also be any laboratory abnormality judged to be clinically significant by the Investigator that worsened when compared to baseline.

AEs include the following:

- All suspected adverse drug reactions.
- All reactions from medication overdose, abuse, withdrawal, sensitivity, or toxicity.
- Apparently unrelated illnesses, including the worsening of a pre-existing illness.
- Injury or accidents.
Note: If a medical condition is known to have caused the injury or accident (e.g., a fall secondary to dizziness), the medical condition (dizziness) and the accident (fall) should be reported as 2 separate AEs.
- Abnormalities in physiological testing or physical examination (findings that require clinical intervention or further investigation beyond ordering a repeat [confirmatory] test).

- Laboratory abnormalities that are clinically significant and require clinical intervention or further investigation (beyond ordering a repeat [confirmatory] test) unless they are associated with an already reported clinical event.

An AE **does not** include:

- Medical or surgical procedures (e.g., surgery, endoscopy, tooth extraction, transfusion); the condition that leads to the procedure is an AE.
- Pre-existing diseases or conditions present or detected at screening/baseline that do not worsen in severity or frequency.
- Situations where an untoward medical occurrence has not occurred (e.g., hospitalization for elective surgery, social and/or convenience admissions).
- Overdose of either study drug or concomitant medication without any signs or symptoms.

Throughout the course of the study, every effort should be made to remain alert to possible AEs. Subjects should be encouraged to report AEs spontaneously or in response to general, non-directed questioning.

With the occurrence of an AE, the primary concern is the safety of the subject. If necessary, appropriate medical intervention should be provided and the study drug discontinued. Urgent safety issues may be discussed with Study Medical Monitor.

7.2. Serious Adverse Events

An SAE is defined as any AE occurring at any dose that results in any of the following outcomes:

- Death.
- A life-threatening AE (i.e., immediate risk of death)
Note: The term “life-threatening” in the definition of “serious” refers to an event in which the subject was at risk of death at the time of the event; it does not refer to an event, which hypothetically might have caused death if it were more severe.
- Prolongation of existing hospitalization or re-hospitalization.
- Results in persistent or significant disability/incapacity.
- A congenital anomaly/birth defect.

Important medical events that may not result in death, be life threatening, or require hospitalization may be considered an SAE when, based upon appropriate medical judgment, the AE may jeopardize the subject and may require medical or surgical intervention to prevent one of the outcomes listed in this definition. Examples of such medical events include allergic bronchospasm requiring intensive treatment in an emergency room or at home; blood dyscrasias or convulsions that do not result in inpatient hospitalization, or the development of drug dependency or drug abuse.

7.3. Adverse Events of Special Interest

AEs of special interest can be either serious or non-serious. For this study, 3 events will be categorized as Special Interest: POI, thrombotic events, and conditions that cause a prolongation of existing hospitalization due to a post-surgical complication. AEs of special interest will be reported as either an SAE (refer to [Section 7.2](#)) or as an AE (refer to [Section 7.1](#)).

7.4. Venous Thrombosis

As indicated in the LB1148 IB, nonclinical toxicology data indicates a possible association between the use of TXA and thrombosis events. However, post-marketing AE reports in humans indicate thromboembolic events are relatively rare. Since TXA is known to have an impact on blood clotting, thrombotic events will be recorded as an AE/SAE and followed to resolution.

7.5. Post-Operative Ileus

Resolution of POI-related symptoms are one of the focuses of this study. As such, any instance of POI will be recorded as an AE/SAE and followed to resolution. POI events post-discharge, but prior to Day 30, will also be recorded as an AE/SAE.

7.6. Post-Surgical Complications

The impact of study drug on LOS is a secondary endpoint for this study. As such, any post-surgical complication that prolongs discharge will be recorded as an AE/SAE.

7.7. Unexpected Adverse Event

An unexpected AE is any AE that is not identified in nature, severity, or frequency in the current LB1148 IB or product information.

7.8. Unexpected Adverse Drug Reaction

An unexpected adverse drug reaction (UADR) is an adverse reaction, the severity of which is not consistent with the applicable product information or IB. All noxious and unintended responses to a medical product related to any dose should be considered an UADR.

- The phrase “responses to a medicinal product” means that a causal relationship between a medicinal product and an AE is at least a reasonable possibility (meaning the relationship cannot be ruled out).
- The expression “causal relationship” is meant to convey that in general there are facts, evidence, or arguments to suggest a reasonable causal relationship. All serious and UADRs will have expedited reporting to regulatory agencies following ICH requirements.

7.9. Adverse Event Reporting Period

AE data will be collected from first administration of study drug through Day 14, Hospital Discharge, or study termination, whichever comes first. Following discharge through the Month 3 visit, any hospital readmissions will be recorded as SAEs.

AEs/SAEs related to the second surgery will also be collected.

If a subject experiences an AE after signing informed consent, but prior to receiving study drug, the event will NOT be collected unless the Investigator feels the event may have been caused by a protocol procedure.

In addition, any known untoward event that occurs subsequent to the AE-reporting period that the Investigator assesses as related to the study drug should also be reported as an AE.

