6.13. Gastrointestinal Function Assessment

Starting on Post-Operative Day 1, GI function will be assessed to determine return of GI function. Daily GI assessments will be collected until either the subject has had return of GI function or Hospital Discharge. If, while still in the hospital, GI function deteriorates to the point of no longer being able to tolerate an oral diet and pass stool, daily measurements should be collected again until the subject has had return of GI function.

Data for this assessment will include but not be limited to:

- Nausea and vomiting (either subject reported or recorded as presence or absence, date and time, including VRS [[Appendix 3](#)]),
- Passing of flatus (either subject reported or Investigator/delegated site personnel reported during a 24-hour calendar day; date and time of first flatus where only the first observance is recorded; in any instance where subject has post-operative complications and experiences ileus as decided by Investigator, the next flatus event should be recorded);
- Passing of stool from anus or ostomy (recorded as presence or absence and date and time);
- Presence of NG/OG tube (including date and time).
- Ability to tolerate liquid diet (liquid diet ordered, subject is able to sustain oral liquid intake without need for IV fluid administration, and total liquid volume over a 24-hour calendar day);
- Ability to tolerate a solid diet (solid diet ordered and date and time of solid food ingestion without significant nausea or vomiting for 4 hours).
- If a subject experiences a POI event during hospitalization, this event will be recorded, including date and time as an AE/SAE.

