6.15. Day 30 Follow-Up

On Day 30 (+7 days), site study staff will contact the subject or their legally authorized representative to determine if the subject experienced a hospital readmission due to GI concerns and/or other medical reasons. If readmission did occur, this event should be recorded as a SAE.

As it is vital to obtain follow-up data, every effort must be made to contact the subject or legally authorized representative to collect this information.

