¹³ Phone call for follow-up to gather any hospital readmission and vital status after initial hospital discharge information. Only readmissions (SAEs) should be recorded and reported.

¹⁴ Only AE/SAEs related to the surgical procedure will be recorded and reported.

¹⁵ Refer to [Error! Reference source not found.](#) for a list of Laboratory Tests. Labs are collected on Screening and Post-Operative Day 3. Post-Operative Day 7 labs will only need to be performed only if subject is still hospitalized.

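### Protocol 7.5 requires ileus after discharge and before Day 30 to be recorded, but the Day 30 call asks about and records only readmissions, so ileus and bowel obstruction without readmission may be under-counted

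*Protocol*

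**What the plan says.** **General AE window.** Protocol 7.9, like the opening of Section 7, says: "AE data will be collected from first administration of study drug through Day 14, Hospital Discharge, or study termination, whichever comes first". After discharge, Section 7 provides for readmissions: "Following discharge through the second surgery visit, any hospital readmissions will be recorded as SAEs". Section 7.9 has a similar sentence but ends the period at a Month 3 visit. Section 7.13 also names Month 3.

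**Ileus.** Section 7.5 adds a specific duty: "POI events post-discharge, but prior to Day 30, will also be recorded as an AE/SAE". It sets no readmission condition. Section 6.13 covers the inpatient period: "If a subject experiences a POI event during hospitalization, this event will be recorded, including date and time as an AE/SAE".

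**Day 30 contact.** Under 6.15, site staff contact the subject "to determine if the subject experienced a hospital readmission due to GI concerns and/or other medical reasons". Footnote 13 of Appendix 1, attached to the Day 30 AE entry, describes it thus: "Phone call for follow-up to gather any hospital readmission and vital status after initial hospital discharge information". It continues: "Only readmissions (SAEs) should be recorded and reported".

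**Second surgery.** Under 6.16, "the site study staff will determine if the subject experienced a hospital readmission due to GI concerns and/or other medical reasons". Footnote 14 confines AE recording at that visit to events related to the surgical procedure.

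**What the data are for.** Protocol 2.1.3 has an exploratory objective on bowel obstruction through 30 days, repeated in SAP 3.3. SAP 11.2.2 defines POI after discharge as a parameter identified by AE preferred term. SAP 11.3 identifies bowel obstruction from AE preferred terms, as a listing.

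**The concern.** Section 7.5 and footnote 13 give a site opposite instructions about the same event. A subject who goes home, develops ileus before Day 30 and is managed without readmission must have the event recorded under 7.5. A site that follows footnote 13 does not record it, and a site that follows 6.15 does not ask.

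Bowel obstruction is less protected still. It has a 30-day objective, but no clause like 7.5 extends its recording past the general AE window.

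POI is one of the protocol's own events of special interest (7.3). If the AE record is the only source and nobody is scheduled to ask, a zero in the output could mean either that no event occurred or that none was looked for.

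**Working it through.** The plan states no figure that depends on this point, so the check is a comparison of passages followed by tracing one event through them.

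**Step 1. The passages side by side, for an event after discharge and before Day 30 with no readmission**

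| Source | POI | Bowel obstruction |
|---|---|---|
| 7, 7.9 general window | Closed by discharge at the latest | Closed by discharge at the latest |
| 6.13 GI assessment | Inpatient only | Inpatient only |
| 7.5 | Must be recorded | No equivalent clause |
| 6.15 Day 30 contact | Not asked | Not asked |
| Footnote 13 | Not to be recorded | Not to be recorded |
| 6.16, footnote 14 (second surgery) | Readmission asked; AEs only if related to the procedure | Same |
| 6.5, Appendix 1 concomitant medications | Collection has ended; no Day 30 entry | Same |

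For POI, 7.5 and footnote 13 cannot both be followed. For bowel obstruction nothing contradicts footnote 13 directly, but the 30-day objective is left without a collection step unless the subject is readmitted.

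**Step 2. Into the analysis**

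- SAP 11.2.2: POI after discharge is identified by AE preferred term alone. The term list includes several bowel obstruction terms, so an unrecorded obstruction is lost from this parameter as well.
- SAP 11.5: POI after discharge has no Cox or Kaplan-Meier analysis. It is included in the frequency table for POI within 14 days, for the mITT population.
- SAP 11.3: bowel obstruction is listing only.
- SAP 4.2: all p-values are nominal.

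**Step 3. Size**

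Let f be the share of post-discharge events that involve no readmission and are not captured by any other route. Then

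recorded incidence = (1 − f) × true incidence.

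The documents give neither f nor a true incidence, so the under-count cannot be computed.

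What can be stated is the weight of one case. SAP 4.3 expects at least 30 randomized subjects from up to 40 enrolled, allocated 1:1. Assuming that 30 to 40 subjects are randomized and all enter the mITT population, each arm has 30/2 = 15 to 40/2 = 20 subjects. One unrecorded case then lowers that arm's proportion by 1/20 = 5.0 to 1/15 = 6.7 percentage points. This is the leverage of a single event, not an estimate of how many are missed.

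**The case against.** The strongest reply is that the plan has other routes.

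- Section 7.1 asks sites to stay alert to AEs throughout the study and to encourage reports through general, non-directed questioning.
- Section 7.9 takes in later events that become known and are judged related to study drug.
- Section 7.13 covers SAEs whatever their cause, and 7.2 lets an important medical event count as serious without hospitalization.
- Protocol 3.1 and SAP section 2 describe AE assessment on Day 30, and Appendix 1 marks an AE entry there.
- Section 7.5 is the more specific rule and can be read as adding to the window in 7.9. On that reading 7.9 is the weaker part of the conflict, and the real contradiction is between 7.5 and footnote 13.

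All of this stands, and it is why the conclusion is that events *may* be missed. None of these routes schedules a question about ileus or obstruction without readmission, and footnote 13 restricts the very Day 30 entry that 3.1 relies on.

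A reader might infer more than the documents support:

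- *That everyone is followed for readmission only from Day 14 to Day 30.* Not so. GI assessment under 6.13 has no Day 14 stop for a subject still in hospital, and 7.6 records complications that prolong discharge.
- *That thrombotic events without readmission are not reportable.* Section 7.4 requires recording with no time limit. What is absent is a prompt at Day 30.
- *That the treatment comparison is biased.* Subjects and sites are blinded (5.5), and nothing shows a different capture rate by arm.
- *That the Cox and Kaplan-Meier analyses of POI within 14 days are affected.* The SAP does not say clearly where an imaging-confirmed ileus after an early discharge but within 14 days would be counted, so this is not established.
- *That past subjects were in fact asked only about readmission.* The call script is not in the documents, and sites may have followed 7.5.

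**Conclusion.** The contradiction is in current text and should be fixed, but its consequence is limited. POI after discharge and bowel obstruction through 30 days may be under-counted when the subject is not readmitted. Events that do lead to readmission are asked about at Day 30 and again at the second surgery.

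The amount cannot be derived from the documents. The affected efficacy outputs are one frequency-table entry and one listing; the AE tables in SAP 12.1 would carry the same omission and are also descriptive. The primary adhesion endpoint does not depend on these records. The conclusion assumes that at least some sites follow 6.15 and footnote 13 as written.

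Two lesser mismatches belong with it. Protocol 3.1 and SAP section 2 place physical examination, vital signs and laboratory tests on Day 30, whereas Appendix 1 shows only the AE entry made by phone, and 6.7.2 has no Day 30 draw. The Month 3 visit in 7.9 and 7.13 is not in the schedule, where the second surgery falls up to 8 months after Day 0.

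**What to change.** 1. Reconcile Protocol 7.5, 7.9, 6.15 and footnote 13 so that the existing Day 30 call asks every subject about ileus and bowel obstruction since discharge, and records such events whether or not the subject was readmitted, noting whether imaging confirmed them. A question on thrombotic events may be added, since 7.4 already requires them to be recorded.
2. Bring the Day 30 text in Protocol 3.1 and SAP section 2 into line with Appendix 1.
3. Replace Month 3 in 7.9 and 7.13 with the second surgery visit, as in Section 7.
4. In the SAP, state that ascertainment after discharge may differ for subjects whose Day 30 call came before the change. Confirm first what sites actually asked.

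The cost is protocol wording, two questions on a call already scheduled, slightly longer calls, more AEs to code and a note in the SAP. There are two analytic downsides. The change cannot reach subjects already past Day 30, so ascertainment would be mixed over time. Post-discharge events identified by AE term would also sit in the same table as events within 14 days, for which SAP 11.2.2 requires confirmatory imaging. Recording imaging status lets the two be told apart.
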